### **7. DISCONTINUATION OF STUDY INTERVENTION AND PARTICIPANT DISCONTINUATION/WITHDRAWAL**

#### **7.1. Discontinuation of Study Intervention**

See the respective sub-study [SoA](#) for data to be collected at the time of study treatment discontinuation (End of Treatment (EOT) visit assessments) and follow-up and for any further evaluations that need to be completed.

In rare instances, it may be necessary for a participant to permanently discontinue study intervention (definitive discontinuation). Reasons for definitive discontinuation of study intervention may include:

- Objective disease progression;
- Global deterioration of health status requiring discontinuation;
- Unacceptable toxicity;
- Pregnancy;
- Significant protocol violation;
- Lost to follow-up;

- Participant refused further treatment;
- Study terminated by sponsor;
- Death.

The discontinuation of study intervention is defined as the discontinuation of all the assigned study drugs.

Note that discontinuation of study intervention does not represent withdrawal from the study. If study intervention is definitively discontinued, the participant will remain in the study to be evaluated for survival. See the [SoA](#) for data to be collected at the time of discontinuation of study intervention and follow-up for any further evaluations that need to be completed.

In the event of discontinuation of study intervention, it must be documented on the appropriate CRF/in the medical records whether the participant is discontinuing further receipt of study intervention or also from study procedures, posttreatment study follow-up, and/or future collection of additional information.

#### **7.1.1. Treatment after Initial Evidence of Radiological Disease Progression**

Immunotherapeutic agents, such as sasanlimab, may produce anti-tumor effects by potentiating endogenous cancer specific immune responses. The response patterns seen with such an approach may extend beyond the typical time course of responses seen with cytotoxic agents and can manifest as a clinical response after an initial increase in tumor burden or even the appearance of new lesions.

If radiologic imaging shows disease progression after dosing with the investigational product(s), participants may continue to receive investigational products, at the investigator's discretion if the following criteria are met:

- Absence of clinical signs and symptoms (including worsening of laboratory values) of disease progression;
- No decline in ECOG performance status;
- Absence of rapid progression of disease by radiographic imaging;
- Absence of progressive tumor at critical anatomical sites (eg, cord compression) requiring urgent alternative medical intervention.

If the participant is subsequently found to have further disease progression at a subsequent tumor assessment, either radiologically according to RECIST v1.1 or clinically, then treatment with investigational products should be permanently discontinued.

#### **7.1.2. Rechallenge**

Retreatment within the study after permanent discontinuation of treatment is not allowed.

## **7.2. Participant Discontinuation/Withdrawal From the Study**

A participant may withdraw from the study at any time at his/her own request.

Reasons for discontinuation from the study may include:

- Refused further follow-up;
- Lost to follow-up;
- Death;
- Study terminated by sponsor;

If a participant withdraws from the study, he/she may request destruction of any remaining samples taken and not tested, and the investigator must document any such requests in the site study records and notify the sponsor accordingly.

If the participant withdraws from the study and also withdraws consent for disclosure of future information (see Section 7.2.1), no further evaluations should be performed, and no additional data should be collected. The sponsor may retain and continue to use any data collected before such withdrawal of consent.

Lack of completion of all or any of the withdrawal/early termination procedures will not be viewed as protocol deviations so long as the participant's safety was preserved.

### **7.2.1. Withdrawal of Consent**

Participants who request to discontinue receipt of study intervention will remain in the study and must continue to be followed for protocol-specified follow-up procedures. The only exception to this is when a participant specifically withdraws consent for any further contact with him or her or persons previously authorized by the participant to provide this information. Participants should notify the investigator in writing of the decision to withdraw consent from future follow-up, whenever possible. The withdrawal of consent should be explained in detail in the medical records by the investigator, as to whether the withdrawal is only from further receipt of study intervention or also from study procedures and/or posttreatment study follow-up, and entered on the appropriate CRF page. In the event that vital status (whether the participant is alive or dead) is being measured, publicly available information should be used to determine vital status only as appropriately directed in accordance with local law.

### **7.3. Lost to Follow-up**

A participant will be considered lost to follow-up if he or she repeatedly fails to return for scheduled visits and is unable to be contacted by the study site.

The following actions must be taken if a participant fails to return to the clinic for a required study visit:

The site must attempt to contact the participant and reschedule the missed visit as soon as possible and counsel the participant on the importance of maintaining the assigned visit schedule and ascertain whether or not the participant wishes to and/or should continue in the study;

Before a participant is deemed lost to follow-up, the investigator or designee must make every effort to regain contact with the participant (where possible, 3 telephone calls and, if necessary, a certified letter to the participant's last known mailing address or local equivalent methods). These contact attempts should be documented in the participant's medical record;

Should the participant continue to be unreachable, he/she will be considered to have withdrawn from the study.

Discontinuation of specific sites or of the study is handled as part of [Section 10.1](#).

## **8. STUDY ASSESSMENTS AND PROCEDURES**

The investigator (or an appropriate delegate at the investigator site) must obtain a signed and dated ICD before performing any study-specific procedures.

Study procedures and their timing are summarized in the respective sub-study [SoA](#). Protocol waivers or exemptions are not allowed.

Safety issues should be discussed with the sponsor immediately upon occurrence or awareness to determine whether the participant should continue or discontinue study intervention.

Adherence to the study design requirements, including those specified in the [SoA](#), is essential and required for study conduct.

All screening evaluations and applicable Cycle 1 Day 1 evaluations must be completed and reviewed to confirm that potential participants meet all eligibility criteria. The investigator will maintain a screening log to record details of all participants screened and to confirm eligibility or record reasons for screening failure, as applicable.

Procedures conducted as part of the participant's routine clinical management (eg, blood count) and obtained before signing of the ICD may be utilized for screening or baseline purposes provided the procedures met the protocol-specified criteria and were performed within the time frame defined in the [SoA](#).

Every effort should be made to ensure that protocol-required tests and procedures are completed as described. However, it is anticipated that from time to time there may be circumstances outside the control of the investigator that may make it unfeasible to perform the test. In these cases, the investigator must take all steps necessary to ensure the safety and well-being of the participant. When a protocol-required test cannot be performed, the

investigator will document the reason for the missed test and any corrective and preventive actions that he or she has taken to ensure that required processes are adhered to as soon as possible. The study team must be informed of these incidents in a timely manner. Guidance for handling protocol-required tests and procedures in public emergencies is provided in [Section 10.12](#).

For samples being collected and shipped, detailed collection, processing, storage, and shipment instructions and contact information will be provided to the investigator site prior to initiation of the study.

## **8.1. Efficacy Assessments**

### **8.1.1. Tumor Response Assessment**

RECIST version 1.1 (see [Section 10.9](#)) will be applied by the site as the primary measure of tumor assessment and response and as the basis for protocol guidelines related to disease status (eg, discontinuation of study treatment).

Radiological scans of all suspected sites of disease will be performed utilizing the same method and technique throughout the study. Target lesions should demonstrate the participant's baseline tumor burden and will be selected based on size (i.e., lesions with the longest diameter), and suitability for accurate repeat assessment.

The following should be performed at Screening/baseline:

- Chest, abdomen, and pelvis CT or MRI scans are required for all participants at Screening.
- An MRI of the brain is also required for all participants at Screening. A CT scan of the brain, preferably with IV contrast, may be performed if MRI is contraindicated. Additional imaging of anatomical sites (eg, head, neck, etc.) should be performed as applicable based on location of disease sites.
- Bone imaging using bone scan (bone scintigraphy), F-FDG-PET, MRI, or other methods considered standard of care locally is required at baseline only if bone metastases are known or suspected outside the body areas scanned using other techniques.
- Radiographic assessments obtained per the participant's standard of care prior to enrollment into the study do not need to be repeated and are acceptable to be used as the Screening/baseline evaluation, if, (1) obtained within 28 days prior to first dose of study treatment, (2) performed using the method requirements (ie, RECIST v. 1.1 ), (3) the same technique/modality can be used to follow identified lesions throughout the trial for a given participant, and (4) appropriate documentation indicating that these radiographic tumor assessments were performed as standard of care is available in the participant's source notes.

The following should be performed during the study/postbaseline:

- During the study chest, abdomen, and pelvis CT or MRI scans are required for all participants. Additional imaging of anatomical sites (eg, head, neck, etc.) should be performed as applicable based on location of disease sites.
- Subsequent MRIs of the brain will only be performed if there were lesions present at baseline or if new brain metastases are suspected.
- If bone lesions are present at baseline, bone imaging should be performed every 12 weeks for the first year and every 24 weeks thereafter. Bone imaging is also required at the time of confirmation of CR for participants who have bone metastases. Otherwise, bone imaging is required only if new bone metastases are suspected.
- Additional imaging evaluations may be performed at any time if there is symptomatic evidence suggesting the possibility of disease progression based on clinical symptoms or physical examination.

Chest X-ray or ultrasound should not be used for tumor response assessments in this study.

While  $^{18}\text{F}$ -FDG-PET scans are not required for this study, sites may perform combined PET/CT scans per their local standard of care, provided the CT is of similar diagnostic quality as CT performed without PET, including the use of oral and IV contrast media. If acquired according to local standard of care  $^{18}\text{F}$ -FDG-PET may be relied upon to document PD in accordance with RECIST.

For participants with known CT contrast allergy, a non-contrast CT of the chest with contrast enhanced abdominal and pelvic MRI can be used. The same imaging technique used to characterize each identified and reported lesion at baseline will be employed in the subsequent tumor assessments. If the imaging technique is changed due to unavoidable circumstances, as assessed by radiologist/investigator, and a comparable measurement of lesion is feasible then the tumor measurement should be reported, otherwise the lesion should be reported as non-evaluable.

CT or MRI scans must be completed before tumor biopsy samples are collected.

Anti-tumor activity will be assessed through radiological tumor assessments conducted at following occasions:

- At timepoints specified in the [SoA](#).
- Whenever disease progression is suspected (eg, symptomatic deterioration).
- After first occurrence of PR or CR is observed according to RECIST v1.1, repeat imaging at least 4 weeks after initial documentation.

- At the time of withdrawal from treatment if not done in the previous 8 weeks and prior response if other than PD.

Measurable or evaluable lesions that have been previously irradiated will not be considered target lesions unless increase in size has been observed following completion of radiation therapy.

All participants' files and radiologic images must be available for source verification and for potential peer review. Radiologic images must be made available to a central vendor, if specified in the respective sub-study appendix, for potential central imaging reading.

For participants who did not end treatment due to disease progression, or withdrawal of consent, a tumor assessment will be performed as per [SoA](#), post the EOT visit, until disease progression by RECIST v1.1, or initiation of a new anti-cancer treatment, or end of study, whichever is first.

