### **New Lesions**

The appearance of any new unequivocal malignant lesion indicates PD. If a new lesion is equivocal, for example due to its small size, continued assessment will clarify the etiology. If repeat assessments confirm the lesion, then progression should be recorded on the date of the initial assessment. A lesion identified in an area not previously scanned will be considered a new lesion.

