## Phase 2:

Primary Estimand (Durable OR): the treatment effect of sasanlimab + encorafenib + binimetinib assessed by the Durable ORR, based on Investigator assessment per RECIST v1.1, in the analysis population.

- Variable: Durable objective response defined as confirmed CR or PR according to RECIST v1.1 based on investigator assessment, lasting for at least 10 months from the date of first CR or PR until the date of the first documentation of PD, death, or start of new anticancer therapy. Both CR and PR must be confirmed by repeat assessments performed no less than 4 weeks after the criteria for response are first met.
- Analysis population: all participants who received at least 1 dose of study drug without regard to tolerability or duration of treatment.
- Population-level summary measure: Durable ORR defined as the proportion of participants in the analysis population with durable OR and 2-sided 95% CI for durable ORR using the Clopper-Pearson method. Participants who do not have a post-baseline tumor assessment due to early progression of disease, who receive anti-cancer therapies other than the study treatments prior to reaching a CR or PR for 10 months, or who die, have PD, or stop tumor assessments for any reason prior to reaching a CR or PR for 10 months will be counted as non-responders in the assessment of durable OR. Each participant will have a durable objective response status (0: no durable OR; 1: durable OR).

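### Section 8.1.1 sets different triggers for bone imaging at baseline and on study, so a lesion that predates treatment can be scored as new and as progression

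*Protocol*

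**What the plan says.** **At baseline (Section 8.1.1).** The body field is fixed for everyone: "Chest, abdomen, and pelvis CT or MRI scans are required for all participants at Screening". A brain MRI is added for all, and other sites are imaged according to where disease lies. Bone imaging by bone scan, FDG-PET, MRI or another locally standard method "is required at baseline only if bone metastases are known or suspected outside the body areas scanned using other techniques".

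**On study (Section 8.1.1).** "If bone lesions are present at baseline, bone imaging should be performed every 12 weeks for the first year and every 24 weeks thereafter". In addition, "Bone imaging is also required at the time of confirmation of CR for participants who have bone metastases". Neither sentence restricts the requirement by location of the lesion. Participants without bone lesions have bone imaging only when new bone metastases are suspected.

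**Scoring (Section 10.9, New Lesions).** "A lesion identified in an area not previously scanned will be considered a new lesion", and "The appearance of any new unequivocal malignant lesion indicates PD". The objective-status table in the same appendix gives PD for any unequivocal new lesion, whatever the target and non-target status.

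**Endpoint (Section 12.3, Phase 2 estimand for Sub-Study A).** Participants "or who die, have PD, or stop tumor assessments for any reason prior to reaching a CR or PR for 10 months" are non-responders for durable OR. PD is also an event for DR and PFS in both sub-studies, and Sub-Study B takes its tumor assessment rules from Section 8.1.1.

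**The concern.** The baseline trigger depends on where the bone disease lies; the on-study trigger depends only on whether there is any. Between them falls a group that has no bone imaging before treatment and must have it during treatment. For this group the first bone image is not compared with an earlier one. A lesion that was present before the first dose but lay outside the CT/MRI field is then read, by rule, as having appeared on treatment.

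The timing matters in Sub-Study A. Scheduled bone imaging starts nominally at week 12, while a durable response must last 10 months. A false PD at the first bone image would end a response well before it could qualify. The error cannot work in the drug's favor.

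The protocol handles the brain differently. Brain MRI is required for everyone at screening and repeated only if lesions were seen or are suspected, so a follow-up brain image always has a baseline. Bone imaging lacks that safeguard.

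**Working it through.** The point rests on no figure in the plan, so the check is a comparison of the rules, followed by a calculation of scale.

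**1. Who is caught.**

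| Bone status at screening | Bone imaging at baseline? | Scheduled bone imaging on study? | Baseline to compare with? |
|---|---|---|---|
| No known or suspected bone lesion | No | No, only on suspicion | No, if later imaged |
| Bone lesion known or suspected outside the scanned field | Yes | Yes, if a lesion is present | Yes |
| Bone lesion only inside the scanned field, none suspected elsewhere | **No** | **Yes** | **No** |

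The third row is the mismatch. It applies equally to the CR-confirmation image.

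**2. What must coincide for a false PD.** (a) The participant is in the third row; (b) the bone-imaging method covers more of the body than the baseline scans; (c) an unsuspected lesion lies in the extra area, for example a limb; (d) it is judged unequivocally malignant. Section 10.9 then makes it new, and therefore PD. No sentence exempts a first bone image or makes it a new baseline. An equivocal lesion is followed, but a lesion confirmed on repeat is recorded as progression at the first date, so a persisting old lesion may end the same way.

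**3. Scale.** The protocol gives no rate for any of these steps. The proportions below are assumptions, shown as low, middle and high:

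- bone lesions at entry: 20%, 30%, 40%;
- of those, no baseline bone imaging because all lesions are in the field: 40%, 60%, 80%;
- of those, an undetected lesion outside the field: 5%, 15%, 25%.

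Fraction affected = product of the three:

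- low: 0.20 × 0.40 × 0.05 = 0.004;
- middle: 0.30 × 0.60 × 0.15 = 0.027;
- high: 0.40 × 0.80 × 0.25 = 0.08.

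Among the 62 participants of Sub-Study A Phase 2 this is 0.25, 1.67 and 4.96 people. The product treats steps (b) and (d) as certain, so within each set of assumptions it overstates the count.

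**4. Effect on the decision rule, for context.** Section 12.9.1.3.2 rejects the null with at least 30 durable responders of 62, with a design alternative of 55%. If a share q of true durable responders is scored PD in error, the observed rate is 0.55 × (1 − q), and the chance of success is the exact binomial P(X ≥ 30 | 62, 0.55 × (1 − q)).

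| q | Observed durable ORR | P(X ≥ 30) |
|---|---|---|
| 0 | 55.0% | 0.880 |
| 0.4% | 54.8% | 0.873 |
| 2.7% | 53.5% | 0.826 |
| 8% | 50.6% | 0.683 |

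The first row is the reference for this table. It differs from the power of at least 90% stated in that section; that is a separate matter and does not bear on this point.

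**The case against.** The strongest reply is that the protocol never calls for whole-body bone imaging. MRI and other local methods are allowed, and "The same imaging technique used to characterize each identified and reported lesion at baseline will be employed in the subsequent tumor assessments". On that reading a vertebral or pelvic lesion characterized on CT is simply followed on CT, and no unscanned area is ever opened. This stands in part: the problem arises only where the method reaches beyond the baseline field. It does not remove the mismatch. The same-technique rule governs lesions already identified, and it does not cancel the separate instruction to perform bone imaging on a 12-week cycle distinct from the CT schedule.

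Other limits also stand.

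- Known or suspected disease outside the field is imaged at baseline, and brain MRI partly covers the skull. Only unsuspected lesions elsewhere remain.
- The lesion must be unequivocally malignant.
- Section 10.9 says that statuses after an inadequate baseline should generally be inevaluable. That is a competing rule, but the status table still gives PD for an unequivocal new lesion.
- A site may choose to image bone at baseline, though nothing requires it.

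Three stronger readings are tempting, and the protocol supports none of them. First, that every old lesion outside the CT field becomes PD: the conditions above are needed. Second, that participants without bone lesions are untouched: they escape the scheduled scans, but the same new-lesion rule applies if they are later imaged on suspicion. Third, that a false PD takes participants off treatment: Section 7.1.1 allows treatment to continue after initial radiological progression when its criteria are met.

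**Conclusion.** The two triggers in Section 8.1.1 do not match, and Section 10.9 can turn the gap into progression. Followed as written, the plan can misclassify a pre-existing lesion outside the baseline field as PD. The direction is certain: durable OR, DR and PFS can only be lowered, mainly in participants with bone lesions.

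The size is not established. The assumed range of 0.4% to 8% of participants comes from outside the protocol. Its upper end sets all three proportions at their worst together, and the product ignores the conditions on method and certainty. The effect is probably small. A reader might infer from the last row of the second table that the trial loses substantial power; that row is a bound under assumptions, not a forecast. The case for a change rests on the contradiction in the text and the low cost of removing it.

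**What to change.** Use one trigger in Section 8.1.1. Limit both the scheduled on-study bone imaging and the bone imaging at confirmation of CR to participants who had bone imaging at baseline. State that bone lesions inside the CT/MRI field are followed on that same CT/MRI, in line with the same-technique rule already in the section. Changing only the scheduled scans would leave the mismatch in place at CR confirmation.

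The cost is a short wording change and fewer scans. The downside is that silent lesions outside the field are sought only on suspicion, as already holds for participants without bone lesions.

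Requiring baseline bone imaging for every participant with a bone lesion would also align the triggers, but it adds procedures. The RECIST new-lesion rule in Section 10.9 should be left unchanged; with matched triggers the scheduled and CR-confirmation scans no longer produce the problem.
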